One treatment cycle will constitute 21 days. DTIC will be administered on Day 1 of each 3-week treatment cycle. Unesbulin/placebo tablets will be administered on Days 2 and 5 of Week 1 and Days 1 and 4 of Weeks 2 and 3 of each 3-week treatment cycle (Note: the preferable duration between 2 doses of unesbulin/placebo is approximately 72 hours). Approximately 12 randomized subjects will be assessed for PK of unesbulin, DTIC, and AIC (an inactive metabolite of DTIC). For Cycles 1 and 3, rich PK sampling will occur on Day 1 for DTIC and AIC, and on Day 2 for unesbulin. The target is for approximately 7 PK evaluable subjects in the unesbulin group to complete Cycle 3. For Cycles 2 and 4, sparse PK sampling will occur on Day 1 for DTIC and AIC.

All subjects will receive treatment until evidence of disease progression, unacceptable toxicity, or other withdrawal criteria are met. No crossover will be permitted.

An independent Data Monitoring Committee (DMC) has been established and will review safety data as per the DMC charter. In addition, one interim efficacy analysis will be performed (by an external vendor) and reviewed by the DMC. Based on the results of this interim analysis, the DMC will make recommendations to either continue or stop the study. The DMC Charter (a separate document) and the DMC Statistical Analysis Plan (SAP) will provide detailed guidance for the conduct of this interim analysis.

Dose modifications/stopping criteria:

If treatment-related toxicities are observed, a stepped reduction in the dose of DTIC is permitted beginning with the starting dose of 1000 to 850 mg/m^2 , followed by 700, 600, and 500 mg/m². The following guidelines should be observed:

- If a subject requires a dose reduction of DTIC to less than 500 mg/m², then DTIC should be discontinued.
- Subjects should receive all necessary supportive care including blood products, platelet transfusions, antiemetics, and antibiotics while being treated on this study.
- The use of granulocyte colony-stimulating factor (eg, pegfilgrastim) and erythropoietin or thrombopoietin-stimulating agents is permitted per institutional practice.

No dose reduction of unesbulin/placebo is permitted. Guidelines for unesbulin/placebo dosing when treatment-related toxicities continue beyond the stepwise dose reduction of DTIC is detailed in this protocol.

Sample Size Justification:

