Laboratory tests include: (1) CBC (hemoglobin, hematocrit, mean corpuscular volume, mean corpuscular hemoglobin, mean corpuscular hemoglobin concentration), WBC count, WBC differential (may be automated or manual as per institutional standards), RBC count, lymphocytes, monocytes, neutrophils, band neutrophils (if reported), eosinophils, basophils, platelets; and (2) CMP: albumin, alkaline phosphatase, total bilirubin, bicarbonate, blood urea nitrogen, calcium, chloride, creatinine, glucose, potassium, total protein, AST, ALT, and sodium.

^h For women of childbearing potential, a serum pregnancy test should be performed at screening (with a window of 7 days) and a urine pregnancy test should be performed within 24 hours of Day 1 of Cycle 1. A urine or serum pregnancy test should be performed within 24 hours prior to dosing on Day 1 of Cycle 2 and continuing every 2 cycles beginning at Cycle 4.

ⁱ For subjects not participating in the PK assessment, a single ECG should be collected on Day 1 of the first 3 treatment cycles only, approximately 2 hours after DTIC infusion. If DTIC is interrupted, then the single ECG should be collected approximately 2 hours after DTIC infusion and recorded on an unscheduled case report form page.

^j For subjects participating in the PK assessment, a single ECG should be taken as follows:

• Predose and 1.5, 4, and 8 hours postdose on Day 1 of Cycles 1 and 3 concurrent with intensive PK sampling for DTIC/AIC.

- Predose and 2, 4, 6, and 8 hours postdose on Day 2 of Cycles 1 and 3 concurrent with intensive PK sampling for unesbulin.
- Approximately 2 hours after DTIC infusion on Cycle 2.

^k Pretreatment, baseline imaging should be performed ≤14 days before Cycle 1 Day 1. On-treatment imaging should be performed every 6 weeks (±7 days). After Cycle 8, scans may be performed every 9 weeks. If any subject responds with a CR or PR at any assessment, then the subsequent confirmatory scan should be performed 4 weeks (+5 days) after the previous scan where the objective response was first evidenced. If the subject withdraws from the study for reasons other than progression of disease, EOT imaging should be performed if the last scan was ≥3 weeks earlier. Subjects should be followed with the same imaging procedure throughout the study. Computed tomography scans or magnetic resonance imaging may be used as clinically indicated.

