One treatment cycle will constitute 21 days. DTIC will be administered on Day 1 of each 3-week treatment cycle. Unesbulin or placebo tablets will be administered on Days 2 and 5 of Week 1 and Days 1 and 4 of Weeks 2 and 3 of each 3-week treatment cycle (Note: the preferable duration between 2 doses of unesbulin/placebo is approximately 72 hours). Based on the results from a food effect assessment in the ongoing Phase 1b Study PTC596-ONC-007-LMS, it is recommended that unesbulin/placebo be administered with food.

All subjects will receive treatment until evidence of disease progression, unacceptable toxicity, or other withdrawal criteria are met. No crossover will be permitted.

Subjects will undergo weekly assessments throughout the study. The schedule of all study efficacy, safety, PK, and laboratory assessments is shown in Table 1, including a window for completion of the activities associated with each visit. Of note, activities designed to be completed in a single day, for example, PK sampling from before dosing to 8 hours postdose, may not be split up between the 2 days of a window.

An end-of-treatment (EOT) assessment should be performed within 30 days after the end of treatment or until recovery from or stabilization of the AE, whichever occurs latest. For subjects requiring immediate initiation of a new treatment option, the EOT visit may be completed earlier. The EOT assessments are outlined in Table 1. A safety follow-up assessment should be performed by telephone call approximately 30 days (\pm 3 days) after the EOT to assess AEs and concomitant medications. Survival follow-up (sFUP) assessments should be performed by phone every 3 months (\pm 7 days) after the EOT until the later of 184 events or 2 years after the last subject is randomized.

PK Assessment

Approximately 12 randomized subjects will participate in a PK substudy at selected sites. These subjects will be assessed for PK of unesbulin, DTIC, and AIC. The target is for approximately 7 PK evaluable subjects in the unesbulin group to complete Cycle 3.

For the DTIC/AIC PK assessment, blood samples will be collected following an intensive schedule at predose and up to 24 hours postdose on Day 1 of Cycles 1 and 3. Sparse blood samples will be collected at predose and 1.25 and 4 hours postdose (start of infusion) on Day 1 of Cycles 2 and 4.

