3.3. Dose Adjustment and Stopping Criteria

Tumor response assessments should continue uninterrupted every 6 to 9 weeks regardless of DTIC dosing/interruptions (see Schedule of Assessments).

Safety laboratory assessments (ie, complete blood count [CBC] and complete metabolic panel [CMP]) will continue as per the Schedule of Assessments regardless of DTIC dosing/interruptions.

The dose of unesbulin/placebo should not be reduced or held. However, any subject who experiences an intolerable toxicity should be withdrawn from the study drug if continuing would place them at risk based on ongoing benefit-risk assessment by the Investigator as described in Section 6.1.2.

If treatment-related toxicities are observed, a stepped reduction in the dose of DTIC is permitted throughout the study, from the starting DTIC dose of 1000 to 850 mg/m², followed by 700, 600, and 500 mg/m². The following guidelines should be observed:

- If a subject requires a dose reduction of DTIC to less than 500 mg/m², then DTIC should be discontinued.
- Subjects should receive all necessary supportive care including blood products, platelet transfusions, antiemetics, and antibiotics while being treated on this study.
- The use of granulocyte colony-stimulating factor (eg, pegfilgrastim) and erythropoietin or thrombopoietin-stimulating agents is permitted per institutional practice and is encouraged prophylactically.

If/when DTIC is on hold, unesbulin/placebo administration should continue uninterrupted BIW. DTIC should be reintroduced as soon as possible upon resolution of the hematological or nonhematological toxicity to a clinically acceptable level. Study staff should adhere to the following steps when DTIC is held due to toxicity during any treatment cycle:

- All procedures should be completed as per the Schedule of Assessments while unesbulin/placebo dosing continues.
- DTIC should be reintroduced at least 48 hours after unesbulin dosing. After DTIC is reintroduced, dosing should continue every 21 days regardless of when it is introduced in a 3-week treatment cycle with unesbulin/placebo. DTIC should not be administered on the same day as unesbulin/placebo dosing.

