5.2. Study Intervention Preparation and Administration

Unesbulin 300 mg or placebo will be administered PO BIW in combination with DTIC 1000 mg/m² administered IV Q21D. Participants should be instructed to not take unesbulin/placebo on the same day as DTIC administration. Additionally, unesbulin/placebo should not be dosed on consecutive days, and preferably at least 3 days (72 hours) between each unesbulin/placebo dose. If a subject misses a dose of unesbulin/placebo, then every attempt should be made to administer within 24 hours. Otherwise, the subject should skip the dose and take unesbulin/placebo at the next scheduled dosing day.

Coadministration of acid-reducing agents should be avoided approximately 4 hours before and after unesbulin/placebo administration.

Placebo tablets will be supplied and administered in a blinded manner to subjects BIW in combination with DTIC per the same dosing schedule as for unesbulin.

Based on the results from a food effect assessment in the ongoing Phase 1b Study PTC596-ONC-007-LMS, it is recommended that unesbulin/placebo be administered with food.

For subjects who cannot swallow the whole tablet, unesbulin/placebo tablets can be dispersed in water at the same dose level at which the tablets are being dosed and be administered orally. The entire dispersion is administered to the subject and taken as soon as possible (within 15 minutes of mixing), ensuring consumption of the entire content with adequate rinsing. Please refer to the Pharmacy Manual for additional details.

If a subject vomits following dosing with unesbulin/placebo, then the unesbulin/placebo tablet may be readministered if the vomiting occurs within 3 minutes of dosing and the tablet contents (white matter) can be seen in the vomitus. If these 2 conditions are not met, then unesbulin/placebo should not be readministered until the next scheduled dosing day.

After DTIC is reconstituted (Section 5.1), the calculated dose of the resulting solution is drawn into a syringe. The reconstituted solution is further diluted with 5% Dextrose Injection, USP or 0.9% Sodium Chloride, USP and administered as an IV infusion over 1 hour ± 30 minutes. Within 30 minutes before DTIC administration, the following premedication regimen is recommended: fosaprepitant 150 mg IV once, dexamethasone 20 mg PO once, and ondansetron

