3.6. Data Definitions and Analysis Issues

3.6.1. Baseline Definition

The Randomization Visit will be defined as Day 1 of the study. For all endpoints, unless otherwise specified, the baseline value will be the latest pre-randomization assessment with a non-missing value, including those from unscheduled visits. If time is not collected, Day 1 assessments are assumed to be taken prior to first dose and used as baseline.

For the purposes of calculating summary statistics of the outcome measures, change from baseline will be derived as follows:

• Change from baseline = post-baseline value – baseline value

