6.5. Electrocardiogram (ECG)

ECG parameters (PR, RR, QRS, QT, QTcF, QTcB) and heart rate (HR) actual value and change from baseline will be summarized by treatment group and the overall population. Each subject's triplicate measurements will be averaged at a given time point before the summary. The number of non-missing values, mean, standard deviation, median, and range (minimum and maximum) will be presented. Change will be calculated as the post baseline measurement minus the baseline measurement. If either the baseline or postbaseline value is missing, the observation will not be included in the change from baseline summary.

In addition, a categorical analysis of QTc intervals will be performed for each time point.

The number and percentage of subjects in each QTc interval (<450 msec, 450-480 msec, 481-500 msec, >500 msec) will be summarized at baseline and each of the subsequent time points.

Categories of changes from baseline (\geq 30 msec and \geq 60 msec), maximum QTc intervals at all post dose time points, and maximum changes from baseline will be summarized by visit.

ECG results (PR, RR, QRS, QT, QTcF, QTcB, and classification of Normality, Abnormality with Clinical Significance, or Abnormality without Clinical Significance) will be presented in data listings.

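### Outside the PK subset, no scheduled on-treatment ECG falls on an unesbulin/placebo day, and the SAP's QTc summaries do not separate DTIC-timed from unesbulin-timed ECGs

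*Protocol*

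**What the plan says.** ECG is a named secondary safety endpoint (Protocol 2.5). For subjects not in the PK assessment, footnote i of the Schedule of Assessments states that "a single ECG should be collected on Day 1 of the first 3 treatment cycles only, approximately 2 hours after DTIC infusion". Table 1 also marks a screening and an end-of-treatment ECG for them.

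Protocol 3.1 fixes the two dosing calendars: "DTIC will be administered on Day 1 of each 3-week treatment cycle", while unesbulin or placebo is "administered on Days 2 and 5 of Week 1 and Days 1 and 4 of Weeks 2 and 3". In cycle days that is 2, 5, 8, 11, 15 and 18. The two may not coincide. Section 3.3 states that "DTIC should not be administered on the same day as unesbulin/placebo dosing", and section 5.2 adds: "Participants should be instructed to not take unesbulin/placebo on the same day as DTIC administration".

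Footnote j gives the PK subset a denser schedule. It includes ECGs predose and 2, 4, 6 and 8 hours after unesbulin/placebo on Day 2 of Cycles 1 and 3.

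SAP 6.5 summarises ECG parameters by treatment group and QTc categories at each time point. For changes of at least 30 and at least 60 msec, and for maxima, it says that "maximum QTc intervals at all post dose time points, and maximum changes from baseline will be summarized by visit". SAP 3.6.1 takes baseline as the latest value before randomization, and then adds: "If time is not collected, Day 1 assessments are assumed to be taken prior to first dose and used as baseline".

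**The concern.** The QTc tables will be read as a comparison of unesbulin plus DTIC with placebo plus DTIC. For nearly all subjects, however, the ECGs behind them are timed to DTIC, which both arms receive, and none is taken within hours of the drug under test. If the question is QTc close to an unesbulin dose, pooling these tracings into one post-dose maximum pulls the comparison toward no difference. The Cycle 1 Day 1 tracing cannot carry any unesbulin effect, because no subject has yet taken unesbulin. Neither document states this limitation, so an unremarkable QTc table could be given more weight than the schedule supports.

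The baseline rule adds a second difficulty. Outside the PK subset, the Cycle 1 Day 1 ECG is scheduled after the DTIC infusion. If its clock time is missing, the SAP makes it the predose baseline.

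**Working it through.** The documents give no power or precision figure for the ECG endpoint, so there is none to reproduce. The check is schedule arithmetic and a simple binomial calculation.

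**Inputs.** ECG days: Table 1, footnotes i and j. Dosing days: Protocol 3.1. Windows of ±2 days (Day 1) and ±1 day (Day 18): Table 1. PK subset of about 12, with about 7 evaluable unesbulin subjects completing Cycle 3: Protocol 3.1. Planned total of about 345: Protocol 3.2. Allocation 2:1: Protocol 5.6.

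**Time from unesbulin to the Day 1 ECG.**
- Cycle 1 Day 1 is study day 1. The first unesbulin dose is on day 2, so there has been no exposure.
- Cycle 2 Day 1 is study day 22 and the last dose is on day 18: 22 − 18 = 4 days = 96 hours.
- Cycle 3 Day 1 is study day 43 and the last dose is on day 39: again 96 hours.
- With windows read as calendar days, the shortest gap is (22 − 2) − (18 + 1) = 1 day and the longest is (22 + 2) − (18 − 1) = 7 days. Table 1 counts windows in business days, so these extremes are approximate. The bar on same-day dosing still keeps the ECG off a dosing day.

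None of the three scheduled on-treatment ECGs is on an unesbulin day, and two of the three follow any unesbulin at all.

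**How each kind of ECG enters the SAP.** SAP 6.5 does not say which drug's dose defines post dose. Elsewhere (SAP 2.3 and 6.1) study drug means unesbulin/placebo or DTIC.

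| ECG | Relation to DTIC | Relation to unesbulin/placebo | Role under the SAP |
|---|---|---|---|
| Non-PK, Cycle 1 Day 1 | about 2 h after | none taken yet | post dose if timed; baseline if untimed |
| Non-PK, Cycles 2–3 Day 1 | about 2 h after | nominally 96 h after | post dose |
| After a DTIC interruption (footnote i) | about 2 h after | at least 48 + 2 = 50 h after (Protocol 3.3) | unscheduled form page; SAP 3.1 keeps unscheduled data out of tables |
| Non-PK, end of treatment | not tied | not tied | post dose |
| PK subset, Day 2 of Cycles 1 and 3 | day after | 2, 4, 6, 8 h after | post dose, not set apart |

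The same Cycle 1 Day 1 tracing can thus be baseline in one subject and post-dose in another, depending only on whether a time was recorded.

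**Size of the informative subset.** Unesbulin arm: 345 × 2/3 = 230. PK subjects on unesbulin: 12 × 2/3 = 8, or 8/230 = 3.5%. The remaining 230 − 8 = 222 unesbulin subjects have no ECG timed to unesbulin.

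**What 8 subjects can show.** Let p be the share of subjects with a QTc outlier within hours of a dose. The documents give no value, so p is an assumption shown over a range. The chance of at least one case among n subjects is 1 − (1 − p)^n.

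| Assumed p | n = 8 | n = 222 |
|---|---|---|
| 1% | 8% | 89% |
| 2% | 15% | 99% |
| 5% | 34% | >99% |
| 10% | 57% | >99% |

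If no subject has an outlier, the exact one-sided 95% upper bound is 1 − 0.05^(1/n). This is 31% for n = 8, 35% for n = 7 and 1.3% for n = 222.

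**Residual exposure at 96 hours.** Protocol 1.2 calls the half-life long but gives no figure. For assumed half-lives h of 12, 24 and 48 hours, the share of the last dose remaining is 2^(−96/h) = 0.4%, 6% and 25%, ignoring what earlier doses add. The Cycle 2 and 3 ECGs may therefore reflect some exposure, but not exposure within hours of a dose.

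**The case against.** The footnote j ECGs belong to the same endpoint. Serial ECGs alongside PK sampling in a subset, with sparse ECGs elsewhere, is a coherent design. A reader might infer that the ECG endpoint cannot show an effect of unesbulin near peak, or that Day 1 is the only cycle day without unesbulin. The documents support neither. PK subjects have up to 4 × 2 = 8 post-unesbulin tracings each, and SAP 6.5 also plans mean-change summaries, so a large or frequent effect could be seen. In the full 21-day cycle, 21 − 6 = 15 days have no dose; Day 1 is unique only among the days listed in Table 1. No Tmax or half-life is given, so even the word peak is an inference from the 2 to 8 hour times in footnote j.

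Three further points have force:
- The safety objective compares regimens, and ECGs after DTIC have a rationale of their own. Protocol 5.5 says DTIC is activated mainly by CYP1A2 and calls unesbulin a strong inhibitor of that enzyme. The comparison is pulled toward no difference only if an effect close to unesbulin dosing is the target.
- SAP 6.5 reports by time point and by visit, so the Day 2 results can be picked out. That does not cover the maximum over all post-dose time points, nor does it supply a caveat.
- The untimed-baseline rule is conditional, and nothing shows that ECG times go unrecorded. Because both arms receive DTIC, any contamination of baseline should be balanced between arms. It would distort change from baseline and the counts at 30 and 60 msec more than the between-arm difference.

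Earlier unesbulin studies and the Investigator's Brochure may hold ECG data close to dosing. The documents do not allow that to be ruled in or out.

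**Conclusion.** The point stands as a limit on interpretation and a defect in SAP wording. Evidence on QTc within hours of an unesbulin dose comes from about 8 planned unesbulin subjects, and a clean result in all 8 would still be compatible with an outlier rate up to 31%. The SAP mixes those ECGs with DTIC-timed ones and can use a post-DTIC tracing as predose baseline.

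The schedule facts rest on no assumption beyond the nominal calendar. The count of 8 assumes that the planned total and the 2:1 split hold within the PK subset. SAP 3.5 reports that the Data Monitoring Committee recommended discontinuing for futility, so the achieved number may differ. The outlier rates and half-lives are illustrative ranges. The documents do not show that unesbulin affects QTc, and this point does not suggest that it does.

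**What to change.** Change the SAP, not the schedule of this trial.

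1. In SAP 3.6.1, exclude ECGs from the rule that untimed Day 1 values are predose baseline. Use the screening ECG or, in PK subjects, the timed predose ECG.
2. In SAP 6.5, do not count Cycle 1 Day 1 ECGs as post-dose in the unesbulin comparison. Label the other Day 1 ECGs as DTIC-timed. Summarise the footnote j Day 2 post-unesbulin ECGs in a separate table by treatment group.
3. In the study report, rest any statement about QTc close to unesbulin dosing on the PK subset only, giving its size and the upper bound.

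The cost is a few sentences and one extra table; no new data are needed. While SAP 6.5 is open, its averaging of triplicate tracings should also be reconciled with the single ECGs that the protocol collects.

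Moving the Cycle 2 and 3 ECGs to the existing Day 8 or Day 15 visits is an option for later protocols only, and it is more than a wording change. Non-PK subjects dose at home, those visits carry a ±2-day window, and neither document says that the diary records clock time. Dose time would have to be captured, the visit coordinated with the dose, and the DTIC-timed ECGs in those cycles given up.

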eCRF	Electronic case report form	
ECOG	Eastern Cooperative Oncology Group	
EOI	End of infusion	
EORTC QLQ-C30	30-item score European Organisation for the Research and Treatment of	
EUNIC QLQ-C30	Cancer Quality-of-Life Questionnaire	
EOT	End-of-treatment	
EQ-5D-5L	EuroQol 5-level EQ-5D version	
FUP	Follow-up	
GCP	Good Clinical Practice	
HRQoL	Health-related quality-of-life	
ICF	Informed consent form	
IEC	Independent Ethics Committee	
IRB	Institutional Review Board	
ITT	Intent-to-treat	
KM	Kaplan-Meier	
LLN	Lower limit of normal	
LLN LMS		
	Leiomyosarcoma Medicel Dictionary for Regulatory Affaire	
	Medical Dictionary for Regulatory Affairs	
mITT	Modified Intent-to-treat	
	National Cancer Institute	
OATP1B1, OATP1B2	Organic anion transporter polypeptide transporters	
ORR	Objective response rate	
OS	Overall survival	

Abbreviation or	Explanation
Specialist Term	
PFS	Progression-free survival
PLT	Platelets
P-gp	P-glycoprotein
PK	Pharmacokinetic/s
PR	Partial response
PRO	Patient-reported outcome
PS	Performance status
PT	Prothrombin time
Q21D	Once every 21 days
RECIST	Response Evaluation Criteria in Solid Tumors
RP2D	Recommended Phase 2 dose
RSI	Reference Safety Information
SAE	Serious adverse event
SAP	Statistical analysis plan
SD	Stable disease
SEER	Surveillance, Epidemiology, and End Results
sFUP	Survival follow-up
SOI	Start of infusion
SOP	Standard operating procedures
SSRI	Selective serotonin reuptake inhibitor
STS	Soft-tissue sarcoma
SUSAR	Suspected unexpected serious adverse reaction
TEAE	Treatment-emergent adverse events
ULN	Upper limit of normal
Vz	Volume of distribution
WBC	White blood cell
WOCBP	Women of childbearing potential

